## 6 STUDY TREATMENT

### 6.1 Baseline Tests and Procedures

Refer to the study calendar in Section [12](#) for requirements prior to initiation of study treatment. The tumor(s) anticipated to receive SRT (and at least one tumor that is measureable and will not be treated with SRT) and disease to be monitored should be identified using assessments completed prior to starting SRT.

## 6.2 Summary of Study Treatment

- Patients will receive a standard treatment regimen of SRT (refer to Section [6.3](#)). The term SRT encompasses all radiotherapy using a stereotactic setup, both stereotactic radiosurgery (SRS) for metastatic lesions in the brain and stereotactic body radiotherapy (SBRT) for SRT delivered to all other locations. Registered patients will be designated as belonging to subgroups as follows:
  - A. Patients receiving SBRT (body) irradiation only
  - B. Patients receiving SBRT and SRS (body and brain) irradiation
  - C. Patients receiving SRS (brain) irradiation only
- The same PD-1 or PD-L1 inhibitor that the patient was receiving prior to study registration will be continued after study registration. The PD-1 or PD-L1 inhibitor will be administered after the last SRT fraction (on the same day) and will continue to be given according to the schedule the patient was receiving prior to study registration through 52 weeks after the last SRT fraction. At the investigator's discretion, administration of the PD-1 or PD-L1 inhibitor may continue during Year 2 or longer (refer to Section [6.4](#) for additional scheduling information).
- At the treating medical oncologist's discretion, one dose of PD-1 or PD-L1 inhibitor may be given after study registration but prior to receiving SRT.
- All doses of the PD-1 or PD-L1 inhibitor administered after study registration will be given at the VCU Massey Cancer Center.

## 6.3 Stereotactic Radiotherapy

For the purposes of data collection and management, only the radiotherapy data required by the eCRFs for this trial will be captured in the database. The radiation treatment plan herein described is standard.

### 6.3.1 Radiation Oncology Department

All study patients will receive SRT in the MCC Radiation Oncology Department.

### 6.3.2 Dose Specifications

- Treatment will be planned to deliver a total of 18 to 60 Gy to the planning target volume (PTV) in up to 10 fractions over 1 to 2 weeks.
- The dose per fraction is to be prescribed so that at least 95% of the PTV receives the prescription dose.

Note: Metastases in different locations may be treated to different doses in the same patient.

### 6.3.3 SRT Treatment Schedule

- SRT must begin **within 4 weeks** following study registration and be completed within 3 weeks after the first SRT fraction.

- The dates of computerized tomography (CT) simulation, start of RT, and completion of RT must be documented.
- The timing of treatment initiation should be coordinated with administration of the PD-1 or PD-L1 inhibitor, which must be given on the same day, after the last SRT fraction.

#### 6.3.4 Treatment Planning

- Planning Constraints

Planning constraints are provided in this section for both the PTV as well as critical normal structures to be spared. Acceptable treatment plans will be established from a DVH-based analysis of the volumetric dose to both the PTV and critical normal structures to ensure that minimally acceptable constraints for each volume of interest have been met.

- Planning Techniques

Planning techniques may differ for each lesion to be treated provided that the tumor motion is properly accounted for with each technique when the target or targets are in or near the thorax region.

- Planning SRT Near Prior Radiotherapy Volumes

The toxicity of delivering SRT to multiple metastases in close proximity to prior conventionally-fractionated external beam RT volumes is not known. Every effort should be made to limit the dose to organs at risk that have previously received radiation.

#### 6.3.5 Technical Factors

- Megavoltage equipment capable of delivering static intensity modulation with a multileaf collimator or dynamic intensity modulation, using a multileaf collimator or tomotherapy, is required.
- Daily image guidance is required. This can take the form of electronic portal imaging, orthogonal KV imaging, or cone beam CT.

#### 6.3.6 Localization, Simulation, and Immobilization

- A custom immobilization device is suggested to minimize set-up uncertainty.
- CT-based simulation (maximum 3 mm slice thickness) is required.

#### 6.3.7 Target Volumes and Contouring

- The gross tumor volume (GTV) is defined as all known gross disease as determined from a combination of clinical and radiographic examination.
- The internal target volume (ITV) is defined as all regions that are likely to harbor microscopic metastatic disease based on location and histology of the tumor and other involved sites as well as compensation for tumor motion.
- Normal structures should be contoured according to consensus guidelines such as Radiation Therapy Oncology Group contouring atlases, if available, or according to other commonly accepted contouring guidelines.

- The PTV will provide a margin around the ITV to compensate for the inter- and intra-fraction uncertainty consequent to daily set-up uncertainty and to potential internal organ motion. Depending on the site of the treated lesion and the immobilization technique used, the PTV will consist of a symmetrical 1-5 mm expansion around the ITV. In the event that PTVs extend outside of the skin surface, the clinician should manually trim the PTV contours to be 3-5 mm inside the outer skin (unless there is direct skin involvement).

#### 6.3.8 Critical Structure Constraints

- Critical structure constraints will be specified according to the American Association of Physicists in Medicine Task Group (AAPM TG101) report ([93](#)). In the event that constraints for the number of fractions used are not listed in the report, dose constraints will be linearly interpolated from TG101 constraints.
- Use TG101 as a guide for dose limits to normal tissue. At a minimum, no organ at risk should receive greater than 105% of the prescription dose.
- In the event that a critical structure is encompassed in the PTV, the area of overlap will be limited to 105% of the prescription dose.

#### 6.3.9 Metastasis Location Definition for Treatment Planning

Each metastasis targeted with SRT will be assigned to one of the 8 “Metastasis Locations” as described in this section.

##### 6.3.9.1 Lung Central

- GTV within 2 cm of proximal bronchial tree: Tumor within or touching the zone of the proximal bronchial tree, defined as a volume 2 cm in all directions around the proximal bronchial tree (carina, right and left main bronchi, right and left upper lobe bronchi, intermedius bronchus, right middle lobe bronchus, lingular bronchus, right and left lower lobe bronchi)
- Tumors that are immediately adjacent to mediastinal or pericardial pleura (ie, PTV touching the pleura) also are considered central tumors

##### 6.3.9.2 Lung Peripheral

Metastases within the lung parenchyma with GTV outside of the proximal bronchial tree as described above

##### 6.3.9.3 Mediastinal/Cervical Lymph Nodes

- Mediastinal  
GTV arising within the anatomic space between the lungs, above the diaphragm, and below the thoracic inlet at the level of the top of the sternal notch
- Cervical lymph nodes  
GTV occurring within cervical lymph node Levels I-VI and/or retropharyngeal spaces; superior border skull base
- Sternal metastases

Assigned to the mediastinal/cervical lymph node location based on potential for normal tissue toxicity

#### 6.3.9.4 Liver

- GTV arising within the liver
- Rib metastases immediately adjacent to the liver assigned to the liver metastasis location

#### 6.3.9.5 Spinal

- Metastases assigned to the spinal/paraspinal site if the GTV arises within the vertebral bodies expanded by 1 cm. Spinal metastases can involve the vertebral body only **or** the vertebral body and pedicle **or** posterior elements only.

For each of these metastases, the PTV delineation will include:

- Involved vertebral body and both pedicles **or**
- More generous delineation of the involved vertebral body and both pedicles **or**
- Involved vertebral body, both pedicles, and the anterior and posterior elements of the spine **or**
- Spinous process and laminae

The target volume may be chosen at the discretion of the treating radiation oncologist based on the extent of tumor involvement.

- Spinal metastases with epidural extension will only be included if there is > 3 mm gap between the edge of the epidural metastasis and edge of the spinal cord.
- Metastases arising in the ribs within 1 cm of the edge of the vertebral body should be included in the spinal metastasis location, but osseous metastases planning guidelines are to be used.

#### 6.3.9.6 Osseous

- GTV arising within an osseous structure, part of the axial skeleton, not included in the spinal definition.
- Rib metastases that are within 1 cm of the vertebral bodies are to be classified into the spinal metastasis location given the similar normal tissues at risk.
- Rib/scapular metastases within the thorax adjacent to lung parenchyma are to be classified into the lung metastasis location given the similar normal tissues at risk.
- Rib/osseous metastases adjacent to mediastinal or cervical structures are to be classified into the mediastinal/cervical lymph node location given the similar normal tissues at risk.

- Rib metastases adjacent to the liver are to be classified into the liver location given the similar normal tissues at risk.
- Rib metastases adjacent to the stomach/abdominal wall are to be classified into the intra-abdominal location given the similar normal tissues at risk.
- Sternal metastases are to be considered part of the mediastinal/cervical lymph nodes location given the similar normal tissues at risk.
- Metastases arising in the bones of the skull are to be included in the brain metastasis location but osseous metastases planning guidelines are to be used.

#### 6.3.9.7 Abdominal-pelvic

GTV arising within the anatomic space defined by the diaphragm superiorly, the genitourinary diaphragm inferiorly including the peritoneal and retroperitoneal spaces, not including the liver, osseous, or spinal metastases

#### 6.3.9.8 Brain

- GTV arising within the anatomic space defined by skull base inferiorly, within 1 cm of brain parenchyma, and not including osseous metastases
- If above skull base but not within 1 cm of brain parenchyma, then include as osseous metastasis

#### 6.3.10 Labeling Target Structures

Target structures will be labeled as gross tumor volume (GTV), internal target volume (ITV) if applicable, and planning target volume (PTV). The prescription dose in cGy will follow the structure names separated by an underscore. Each should be labeled according to numerical order of the anatomical sites described in Section [6.3.9](#) (eg, PTV\_5000\_2 is a peripheral lung lesion receiving 50 Gy while PTV\_5000\_4 is a liver lesion receiving 50 Gy). If multiple lesions exist within a single anatomical site, each lesion can be distinguished by adding a letter to the end of the PTV name (eg, PTV\_5000\_1a and PTV\_5000\_1b). Brain lesions can also include an anatomic descriptor (eg, PTV\_2700\_8a\_ left parietal).

#### 6.3.11 Supportive Care

Supportive care for management of symptoms related to SRT is at the discretion of the radiation oncologist.

### 6.4 Administration of the PD-1 or PD-L1 Inhibiting Therapy

The following instructions regarding the administration of the PD-1 or PD-L1 inhibitor will be followed:

#### 6.4.1 PD-1 or PD-L1 Inhibitor

The patient must continue to receive the same PD-1 or PD-L1 inhibitor that had been administered prior to study registration.

#### 6.4.2 Preparation and Administration of the PD-1 or PD-L1 Inhibitor

Refer to the current agent-specific prescribing information for instructions regarding preparation and administration of the PD-1 or PD-L1 inhibitor.

#### 6.4.3 PD-1 or PD-L1 Inhibitor Treatment Schedule

- The timing of the pre-SRT dose of the PD-1 or PD-L1 inhibitor (if given) must be planned to allow the second PD-1 or PD-L1 inhibitor dose to be administered on the last day of SRT (following the last SRT fraction).

Note: Administration of an on-study PD-1 or PD-L1 inhibitor prior to initiation of the SRT is not required, but one pre-SRT dose is permitted. (See Section [4.1.4](#) regarding requirements prior to study registration.)

- The PD-1 or PD-L1 inhibitor will continue to be administered according to the prescribing information for the agent the patient is receiving. At the discretion of the treating medical oncologist, modifications in treatment schedule are permitted.

#### 6.4.4 Duration of PD-1 or PD-L1 Inhibiting Therapy

The PD-1 or PD-L1 inhibitor will continue until 12 months following completion of SRT. At the treating investigator's discretion, the PD-1 or PD-L1 inhibitor may be continued during Year 2 (or longer) if the patient continues to tolerate treatment and is receiving clinical benefit.

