## 6.6 Duration of Therapy

Study treatment will be administered as described in Sections [6.3](#) and [6.4](#) unless one of the following occurs (also see study withdrawal criteria in Section [5.2](#)):

- AE that requires discontinuation of study treatment
- Pregnancy
- Determination by the investigator that discontinuation is in the patient's best medical interest
- Patient decision to discontinue study treatment
- Withdrawal of study sponsor support

The reason for discontinuation of study treatment must be documented in the source documents and in the OnCore database.

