#### 6.7.1.2 AEs Related to PD-1 or PD-L1 Inhibiting Therapy

Assessment and reporting of selected AEs related to the PD-1 or PD-L1 inhibiting therapy as described in Section [8.5.2](#) will continue until the PD-1 or

PD-L1 inhibitor has been discontinued (for any reason) or until 2 years after completion of SRT, whichever occurs first.

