- P. SRT must be administered by VCU Radiation Oncology and must begin within 4 weeks following study registration; refer to Section [6.3](#) for additional SRT requirements and instructions.
- Q. If one dose of the PD-1 or PD-L1 inhibitor needs to be given after study registration (before the first SRT fraction), the pre-SRT dose (if given) must be timed so that the next dose is given on the same day as the last SRT fraction.
- R. At the discretion of the treating medical oncologist, the PD-1 or PD-L1 inhibitor may continue to be administered after 52 weeks following completion of SRT if there has not been disease progression following SRT.
- S. For patients with post-SRT disease progression, follow-up can be limited to assessment of vital status until 2 years after completion of SRT.

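### For Year 2, section 6.4.4 and Table 5 footnote R disagree on giving the inhibitor after progression, and footnote S lets adverse-event follow-up lapse in patients still on it

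*Combined protocol and SAP*

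**What the plan says.** **Year 1.** Section 6.4.4 states: "The PD-1 or PD-L1 inhibitor will continue until 12 months following completion of SRT". The reasons for stopping study treatment in section 6.6 begin with "AE that requires discontinuation of study treatment" and go on to pregnancy, the investigator's judgement of the patient's best interest, the patient's own decision, and loss of sponsor support. Progression is not on that list, nor on the withdrawal list in section 5.2.

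**Year 2 dosing.** Three places address it:
- Section 6.2, the treatment summary, says that at the investigator's discretion "administration of the PD-1 or PD-L1 inhibitor may continue during Year 2 or longer", and refers to 6.4 for scheduling.
- Section 6.4.4 says that, at the treating investigator's discretion, the drug "may be continued during Year 2 (or longer) if the patient continues to tolerate treatment and is receiving clinical benefit".
- Table 5 footnote R says that, at the treating medical oncologist's discretion, it "may continue to be administered after 52 weeks following completion of SRT if there has not been disease progression following SRT".

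**Safety follow-up.** Section 6.7.1.2 concerns "Assessment and reporting of selected AEs related to the PD-1 or PD-L1 inhibiting therapy". It ends that work at one of two points: "PD-L1 inhibitor has been discontinued (for any reason) or until 2 years after completion of SRT, whichever occurs first". Table 5 footnote E likewise has AEs assessed every 2 to 6 months through Year 2 in patients who stay on the inhibitor. Footnote S reads: "For patients with post-SRT disease progression, follow-up can be limited to assessment of vital status until 2 years after completion of SRT".

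**The concern.** Two questions about the same patient get different answers depending on where the site looks. May a patient who has progressed since SRT, but is thought to be benefiting, receive the inhibitor in Year 2? If so, must AEs still be assessed?

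The second question bears on a stated endpoint. Section 3.4.5 counts immunotherapy-related AEs from 8 weeks to 2 years after SRT that lead to both stopping the inhibitor and starting immunosuppression. It has no cut-off at progression. By definition these events arise in patients who are on the drug. The safety population in 13.5.1 is fixed by having received at least one SRT fraction and at least one inhibitor dose after SRT, so a patient whose follow-up is reduced stays in the denominator. An event not looked for in such a patient lowers the reported rate. Note A to Table 1 ties late expedited reporting of serious AEs to the same recorded events, so a missed event could also go unreported there.

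**Working it through.** The plan gives no figure for this point and no arithmetic applies. The check is a comparison of passages on one test patient: alive at week 52, progressed after SRT, tolerating the inhibitor, judged to be benefiting.

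**Step 1. May the inhibitor continue in Year 2?**

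| Place | Who decides | Condition | Test patient |
|---|---|---|---|
| 6.2 | investigator | none stated | may continue |
| 6.4.4 | treating investigator | tolerance and clinical benefit (benefit not defined) | may continue |
| Footnote R | treating medical oncologist | no progression after SRT | may not continue |

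Sections 6.2 and 6.4.4 permit continuation by silence on progression; footnote R excludes it expressly. Section 6.2 is a summary that points to 6.4, so it is looser than 6.4.4 rather than a separate rule. The direct conflict is 6.4.4 against footnote R.

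**Step 2. If the test patient continues, what follow-up is due?**

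| Place | Trigger | Follow-up |
|---|---|---|
| 6.7.1.2 | on the inhibitor, up to 2 years | selected AEs assessed and reported |
| Footnote E | on the inhibitor in Year 2 | AEs every 2 to 6 months |
| Footnote S | progression after SRT | vital status is enough |

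The test patient meets all three triggers. Section 6.7.1.2 and footnote E are keyed to exposure. Footnote S is keyed to progression and does not exempt patients still exposed. Section 6.7.2 directs that response and survival follow-up run according to Table 5, so its footnotes are operative text.

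**Step 3. Are the two conflicts linked?** Yes. If footnote R governs, no patient who has progressed is on the inhibitor in Year 2. Footnotes E and S then describe separate groups, and the table is coherent. If 6.4.4 governs, the groups overlap and footnote S permits what 6.7.1.2 and footnote E forbid.

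**Step 4. Does the conflict reach Year 1?** No passage makes progression a reason to stop in Year 1, and none says otherwise, so there is no contradiction on dosing. In Table 5 the marker for footnote S appears only in the survival row under Year 2. The AE cells at weeks 16, 24 and 52 carry footnote D, which limits the type of AE and is not tied to progression. The text of footnote S does not state a Year 2 limit, but its position points to one.

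**Step 5. How many patients?** The count would need the share who progress, and the share of those who are alive and still on the inhibitor after week 52. The documents give neither.

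**The case against.** The strongest reply is that Table 5, read on its own, is consistent: footnote R ends dosing for progressed patients in Year 2, footnote S then reduces their follow-up, and footnote E covers those still treated. Footnote S is also only permissive, while AE assessment on drug is stated as a requirement in two places. A careful site would keep assessing. Silent loss is further limited because an AE counted after week 8 must have led to stopping the inhibitor. Section 6.6 requires the reason for stopping to be documented in source and in the OnCore database, and 6.2 has all doses given at the study centre.

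Much of this stands. It shows that missed events are possible, not that they will occur. It does not remove the conflict, because Table 5 is coherent only if footnote R overrides 6.4.4, and nothing says that it does.

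A reader might infer more than the documents support:
- *That there are three rival rules.* Section 6.2 is a looser summary of 6.4.
- *That the plan keeps Year 1 progressors on drug without AE follow-up.* Section 6.6 allows stopping on the investigator's or the patient's decision. Section 6.5.1 bars other cancer treatment only until progression, so some patients can be expected to switch. Footnote S is attached to a Year 2 cell.
- *That a headcount can be given.* An assumed progression share of 40% to 75% of the 42 evaluable patients gives 0.40 × 42 = 16.8 to 0.75 × 42 = 31.5, or about 17 to 32. That share is not in the documents, and the result counts everyone who progresses, including those who have stopped the drug or died.
- *That 2-year survival is compromised.* It is a descriptive, single-arm secondary endpoint, and treatment after progression is already unrestricted under 6.5.1.

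**Conclusion.** The point holds in a limited form. For Year 2, 6.4.4 and footnote R give opposite answers for a patient who has progressed but is judged to benefit, and 6.2 is looser still. If such a patient continues, 6.7.1.2 and footnote E require AE assessment that footnote S allows the site to omit. The exposed part of the plan is the late immunotherapy AE endpoint in 3.4.5, where any error from missed events would be towards too low a rate.

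The size cannot be derived. It could be zero if no progressed patient is treated in Year 2, and it rises with the number who are. The conclusion assumes that footnote S belongs to Year 2, as its position suggests, and that 6.4.4 is not meant to be overridden by footnote R, which the documents do not settle. The 24-week primary endpoint, the two-stage decision rule and the sample size are unaffected. A change is worth making because it is cheap and protects safety data in patients still receiving study drug.

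**What to change.** 1. The investigators should reconcile 6.2, 6.4.4 and footnote R into one statement on whether the inhibitor may continue in Year 2 after progression, naming one decision-maker. Which rule to adopt is for them.
2. Amend footnote S so that reduction to vital status applies only to patients who have stopped the inhibitor and whose AE windows under 6.7.1 have closed, with a cross-reference to footnote E. This is worth doing whichever rule is chosen, since it holds for any patient who is on drug after progression.

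The cost is a wording amendment. The AE checks it secures fall at visits where the drug is being given anyway, and 6.7.1.2 and footnote E already require them.

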#### 6.4.5 Assessment and Management of PD-1 or PD-L1 Inhibiting Therapy Side Effects

Information and instructions found in the applicable prescribing information should be followed. However, management of side effects is at the discretion of the treating medical oncologist.

